#### Liver function and related variables

ALT (SGPT):	> 3 x upper limit of normal (ULN)
AST (SGOT):	> 3 x ULN
Total bilirubin:	> 2 x ULN
Alkaline phosphatase:	> 2 x ULN

## Renal function and electrolyte variables

Creatinine (serum): $> 1.5 \text{ x ULN}$
---

#### Hematology variables

Hemoglobin:	$\geq$ 20 g/dL decrease from Baseline
Platelet count:	< lower limit of normal (LLN)
White blood cell count:	< 0.8 x LLN
Neutrophils:	< 0.9 x LLN
Eosinophils:	> 1.1 x ULN
Lymphocytes:	> 1.1 x ULN

#### Urinalysis variable

Protein urine dipstick:

++\* (\* ++ is  $\geq$  100 mg/dL)

# 16.2 Appendix 2: Liver event and laboratory trigger definitions & follow-up requirements

	Definition/ threshold
Liver laboratory triggers	• $3 \times ULN < ALT / AST \le 5 \times ULN$
	• $1.5 \times \text{ULN} < \text{TBL} \le 2 \times \text{ULN}$
Liver events	• ALT or AST > 5 × ULN
	• ALP > 2 × ULN (in the absence of known bone pathology)
	
 
TBL > 2 × ULN (in the absence of known Gilbert syndrome)
 

	• ALT or AST > 3 × ULN and INR > 1.5
	
 
Potential Hy's Law cases (defined as ALT or AST > 3 × ULN and TBL > 2 × ULN [mainly conjugated fraction] without notable increase in ALP to > 2 × ULN)
 

	Any clinical event of jaundice (or equivalent term)
	
 
ALT or AST > 3 × ULN accompanied by (general) malaise, fatigue, abdominal pain, nausea, or vomiting, or rash with eosinophilia
 

	Any adverse event potentially indicative of a liver toxicity*

#### Table 16-3 Liver event and laboratory trigger definitions

\*These events cover the following: hepatic failure, fibrosis and cirrhosis, and other liver damagerelated conditions; the non-infectious hepatitis; the benign, malignant and unspecified liver neoplasms

ALT=alanine aminotransferase, ALP=alkaline phosphatase, AST=aspartate aminotransferase, INR=international normalized ratio, TBL=total bilirubin, UNL=upper normal limit

Table 16-4	Follow-up requirements for liver events and laboratory triggers	
Criteria	Actions required	Follow-up monitoring
Potential Hy's Law caseª	
 
Discontinue the study treatment immediately
 
	ALT, AST, TBL, Alb, pt/INR, ALP and γGT until resolution c
	Hospitalize, if clinically appropriate	(frequency at investigator
	Establish causality	discretion)
	Complete liver CRF	
ALT or AST		
> 8 × ULN	
 
Discontinue the study treatment immediately
 
	ALT, AST, TBL, Alb, pt/INR, ALP and γGT until resolution c
	Hospitalize if clinically appropriate	(frequency at investigator
	Establish causality	discretion)
	Complete liver CRF	
> 3 × ULN and INR > 1.5	
 
Discontinue the study treatment immediately
 
	ALT, AST, TBL, Alb, pt/INR, ALP and γGT until resolution c
	Hospitalize, if clinically appropriate	(frequency at investigator discretion)
	Establish causality	discretion
	Complete liver CRF	

Table 16-4	Follow-up requirements for liver events and laboratory triggers	
	i onow-up requirements for inver events and laboratory triggers	

Criteria	Actions required	Follow-up monitoring
> 5 to ≤ 8 × ULN	Repeat LFT within 48 hours	ALT, AST, TBL, Alb, pt/INR, ALP
	
 
If elevation persists, continue follow up monitoring
 
	_ and γGT until resolution c (frequency at investigator discretion)
	• If elevation persists for more than 2 weeks, discontinue the study drug	,
	Establish causality	
	Complete liver CRF	
> 3 × ULN accompanied by	
 
Discontinue the study treatment immediately
 
	ALT, AST, TBL, Alb, pt/INR, ALP and γGT until resolution c
symptoms b	Hospitalize if clinically appropriate	(frequency at investigator
	Establish causality	discretion)
	Complete liver CRF	
$> 3 \text{ to } \le 5 \times \text{ULN}$	Repeat LFT within the next week	Investigator discretion
(patient is asymptomatic)	
 
If elevation is confirmed, initiate close observation of the patient
 
	Monitor LFT within 1 to 4 weeks
ALP (isolated)		
> 2 × ULN (in the	Repeat LFT within 48 hours	Investigator discretion
absence of known bone pathology)	
 
If elevation persists, establish causality
 
	Monitor LFT within 1 to 4 weeks o at next visit
	Complete liver CRF	
TBL (isolated)		
> 2 × ULN (in the absence of known Gilbert syndrome)	Repeat LFT within 48 hours	ALT, AST, TBL, Alb, pt/INR, ALP
	If elevation persists, discontinue the study drug immediately	and γGT until resolution c (frequency at investigator discretion)
	Hospitalize if clinically appropriate	Test for hemolysis (e.g.,
	Establish causality	reticulocytes, haptoglobin,
	Complete liver CRF	unconjugated [indirect] bilirubin)
> 1.5 to $\leq$ 2 × ULN	• Repeat LFT within the next week	Investigator discretion
(patient is asymptomatic)	If elevation is confirmed, initiate close observation of the patient	Monitor LFT within 1 to 4 weeks o at next visit
Jaundice	Discontinue the study treatment immediately	ALT, AST, TBL, Alb, pt/INR, ALP and γGT until resolution °
	Hospitalize the patient	(frequency at investigator discretion)
	Establish causality	
	Complete liver CRF	
Any AE potentially indicative of a liver toxicity*	
 
Consider study treatment interruption or discontinuation
 
	Investigator discretion
	Hospitalization if clinically     appropriate	
	Establish causality	
	Complete liver CRF	

b(General) malaise, fatigue, abdominal pain, nausea, or vomiting, or rash with eosinophilia

Criteria Actions required Follow-up monitoring		Follow-up monitoring
c Resolution is defined as an outcome of one of the following: (1) return to baseline values, (2) stable		

values at three subsequent monitoring visits at least 2 weeks apart, (3) remain at elevated level after a maximum of 6 months, (4) liver transplantation, and (5) death.

Alb=albumin, AESI=adverse event of special interest, ALP=alkaline phosphatase, CRF=case report form, INR=international normalized ratio,  $\gamma$ GT=gamma glutamyl transferase, LFT=liver function test, pt=prothrombin time, TBL=total bilirubin, ULN= upper limit of normal

#### 16.3 Appendix 3: GO-QoL assessment

#### GO-Quality Of Life Questionnaire

The following questions deal specifically with your thyroid eye disease. Please focus on the past week while answering these questions.

During the past week, to what extent were you limited in carrying out the following activities, because of your thyroid eye disease?

Tick the box that matches your answer. The boxes correspond with the answers above them. Please tick only one box for each question.

		Yes seriously limited	Yes a little limited	No not at all limited	
1)	Bicycling (never learned to ride a bike□)				
2)	Driving (no driver's licence 🔲)				
3)	Moving around the house				
4)	Walking outdoors				
5)	Reading				
6)	Watching TV				
7)	Hobby or pastime, i.e.				
8)	During the past week, did you feel hindered from something that you wanted to do because of your thyroid eye disease?	Yes severely hindered	Yes a little hindered	No not at all hindered	
~*					Score
The	following questions deal with your thyroid eye disease	in general			
		Yes, very much so	Yes a little	No not at all	
9)	Do you feel that you appearance has changed because of your thyroid eye disease?				
10)	Do you feel that you are stared at in the streets because of thyroid eye disease				
11)	Do you feel that people react unpleasantly because of your thyroid eye disease?				
12)	Do you feel that your thyroid eye disease has an influence on your self-confidence?				
13)	Do you feel socially isolated because of your thyroid eye disease				
14)	Do you feel that your thyroid eye disease has an influence on making friends?				
15)	Do you feel that you appear less often on photos than before you had thyroid eye disease?

SOC	System Organ Class
TEAE(s)	Treatment-Emergent Adverse Event(s)
TED	Thyroid Eye Disease
TFLs	Tables, Figures, Listings

1 Introduction

The purpose of this statistical analysis plan (SAP) is to provide details of the statistical analysis according to Section 12 of the study protocol v02 for AIN457 (secukinumab) Study CAIN457ADE16 dated 15-Mar-2022. The scope of this plan includes the primary and secondary analyses. The purpose of this amendment is to modify the analysis plan to reflect the early termination status of the study. At the time of termination, 28 patients had been randomized, 25 patients had completed the double-blind treatment period, and 23 patients had entered the follow-up period.

1.1 Study design

This is a randomized, placebo-controlled, double-blind, parallel-group, interventional, multicenter study in patients with moderate to severe thyroid eye disease (TED). This study consists of the following 3 periods (see [Figure 1-1](#)):

Screening period (Week -6 to Baseline)

Patients' eligibility will be assessed during the Screening Period, which will occur for a maximum of 6 weeks. In the event of a major healthcare disruption (e.g., a pandemic or epidemic) that limits or prevents on-site visits to the study sites, the Screening Period may be extended to a maximum of 8 weeks before Baseline.

Double-blind treatment period (DBTP) (Baseline to Week 16)

Eligible patients will be randomized in a 1:1 ratio to one of the following double-blinded treatment arms:

- Arm 1: Secukinumab 300 mg s.c. at Baseline, Week 1, 2, 3, 4, 8, 12 (n=35)
- Arm 2: Placebo s.c. at Baseline, Week 1, 2, 3, 4, 8, 12 (n=35)

Patients will be stratified according to current smoking status (up to 20% smokers per arm), since smoking has a well-known impact on treatment efficacy in TED.

Follow-up/open-label retreatment period (Week 16 up to Week 108)

- Proptosis responders (see definition below) at Week 16 will be followed for relapse up to Week 68. If these patients relapse, they will be offered a course of open-label secukinumab at the time of relapse (see "proptosis relapsers" definition below).
- Proptosis non-responders (see definition below) at Week 16 will be offered the option of open-label secukinumab treatment (with maintenance of blind of initial randomized treatment) for a duration of 16 weeks, i.e., up to Week 32 with last dose at Week 28, as follows:

Open-label secukinumab 300 mg s.c. at Week 16, 17, 18, 19, 20, 24 and 28. Thereafter (i.e., from Week 32), patients will be followed up for a further 24 weeks [REDACTED].

For patients who are proptosis non-responders and who do not receive open-label secukinumab treatment, a follow-up visit (End of Study [EOS]) 8 weeks after the Week 16 visit should be scheduled. At this EOS visit, the assessments associated with the Week 24 visit (for responder) should be performed.

- **Proptosis relapsers** (see definition below) during the follow-up period (from Week 16 onward to Week 68) will be offered the option of retreatment with open-label secukinumab for a duration of 16 weeks (with maintenance of blind to initial randomized treatment) at the time of relapse as follows:

Open-label secukinumab 300 mg s.c., at time of relapse, then at 1, 2, 3, 4, 8 and 12 weeks.
[REDACTED]
[REDACTED]

For patients not receiving open-label secukinumab treatment, a follow-up visit (EOS) 8 weeks after the Week 16 visit should be scheduled, if not yet completed. At this EOS visit, the assessments associated with the Week 24 visit (for responder) should be performed.

[figure not shown]
In the event of a major healthcare disruption (e.g., a pandemic or epidemic) that limits or prevents on-site visits, special efforts should be made to conduct the Week 16, R16 and NR16 visits on-site, if feasible. If it is not feasible to conduct these visits on-site, visits to the patient's home, or a virtual visit if a home visit is not feasible, should be attempted.

Definitions of proptosis responder, non-responder and relapser

- **Proptosis responder:** Patients achieving response in reduction of proptosis at Week 16 defined as follows: reduction of ≥ 2 mm from Baseline in the study eye without deterioration (≥ 2 mm increase from Baseline) of proptosis in the fellow eye.
- **Proptosis non-responder:** Patients not achieving response in reduction of proptosis at Week 16 with "response" defined as follows: reduction of ≥ 2 mm from Baseline in the study eye without deterioration (≥ 2 mm increase from Baseline) of proptosis in the fellow eye.
- **Proptosis relapser:** Patients who are "proptosis responders" as defined above, and then relapse based on proptosis [REDACTED] with relapse defined as follows: increase in proptosis of ≥ 2 mm compared to Week 16 in the study eye or deterioration of proptosis (≥ 2 mm increase compared to Week 16) in the fellow eye at any time during 52-week follow-up period.

In case of worsening of the disease during study treatment, patients may receive alternative treatment for TED at the discretion of the investigator and will be discontinued from the study treatment.

Figure 1-1 Study design

1.2 Study objectives and endpoints

The purpose of this study is to demonstrate the efficacy and safety of secukinumab 300 mg s.c. in adults with active, moderate to severe TED.

Due to non-efficacy (no responders at the time of premature study discontinuation), purely descriptive analyses will be performed for primary and secondary endpoints. Exploratory endpoints will not be analyzed.

The objectives and related endpoints are presented in the table below.

Table 1-1 Objectives and related endpoints

Objective	Endpoint
Primary objective	Primary endpoint
1) To demonstrate that secukinumab is superior to placebo with regard to the overall responder rate after 16 weeks of treatment.	1) Proportion of patients achieving overall response defined as: ≥ 2 point reduction in clinical activity score (CAS) AND ≥ 2 mm reduction in proptosis from Baseline in the study eye, provided there is no corresponding deterioration in CAS or proptosis (≥ 2 point or 2 mm increase, respectively) in the fellow eye after 16 weeks of treatment.
Secondary objectives	Secondary endpoints
2.1) To demonstrate that secukinumab is superior to placebo with regard to the CAS responder rate after 16 weeks of treatment.	2.1) Proportion of patients achieving response in reduction of CAS at Week 16 defined as follows: reduction of ≥ 2 points from Baseline in the study eye

Objective	Endpoint
	without deterioration (≥ 2 point increase) of CAS in the fellow eye.
2.2) To demonstrate that secukinumab is superior to placebo with regard to the proptosis responder rate after 16 weeks of treatment.	2.2) Proportion of patients achieving response in reduction of proptosis at Week 16 defined as follows: reduction of ≥ 2 mm from Baseline in the study eye without deterioration (≥ 2 mm increase) of proptosis in the fellow eye.
2.3) To demonstrate that secukinumab is superior to placebo with regard to reduction in diplopia after 16 weeks of treatment.	2.3) Proportion of patients achieving response in diplopia at Week 16 defined as follows: Baseline diplopia > 0 and a reduction of ≥ 1 grade with no corresponding deterioration (≥ 1 grade worsening) in the fellow eye at Week 16.
2.4) To demonstrate that secukinumab is superior to placebo with regard to reduction in CAS after 16 weeks of treatment.	2.4) Mean change from Baseline to Week 16 in CAS in the study eye.
2.5) To demonstrate that secukinumab is superior to placebo with regard to reduction in proptosis after 16 weeks of treatment.	2.5) Mean change from Baseline to Week 16 in proptosis in the study eye.
2.6) To demonstrate that secukinumab is superior to placebo with regard to improvement in disease severity after 16 weeks of treatment.	2.6) Mean change in EUGOGO disease severity from Baseline to Week 16.
2.7) To demonstrate that secukinumab is superior to placebo with regard to improvement in GO-QoL after 16 weeks of treatment.	2.7) Mean change from Baseline to Week 16 in GO-QoL score.
Safety (secondary) endpoint	Safety (secondary) endpoint
2.8) To evaluate the safety of secukinumab 300 mg s.c. compared to placebo.	2.8) Frequency of AEs, TEAEs, AEs resulting in treatment discontinuation, SAEs.

2 Statistical methods

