### 5.1 Inclusion criteria

Patients eligible for inclusion in this study must meet all of the following criteria:

- 1. Patient must be able to understand and communicate with the investigator and comply with the requirements of the study and must give a written, signed and dated informed consent before any study assessment is performed.
- 2. Male or non-pregnant, non-lactating female patients  $\geq 18$  years of age.
- 3. Clinical diagnosis of active, moderate to severe TED (not sight-threatening) in the study eye at Baseline associated with two or more of the following:
  - Lid retraction  $\geq 2$  mm.
  - Moderate or severe soft tissue involvement.
  - Exophthalmos  $\geq$  3 mm above normal
  - Inconstant or constant diplopia.
- 4. Onset of TED symptoms fewer than 12 months prior to Baseline.
- 5. Clinical activity score  $(CAS) \ge 4$  (on a 7-point scale, with a score of  $\ge 3$  indicating active TED) in the more severely affected (study) eye at Screening and Baseline. (Proptosis is the primary qualifier for selection of the study eye. In case both eyes show a similar degree of proptosis, other inflammatory signs and symptoms (CAS) should be taken into account by the investigator for the selection of the study eye).
- 6. Peripheral euthyroidism or mild hypo-/hyperthyroidism defined as fT3 and fT4 < 30% above/below normal limits at Screening. Every effort should be made to correct the mild hypo-/hyperthyroidism promptly and to strictly maintain the euthyroid state until the end of this study.

Note: Central lab retests will be allowed during the Screening Period (day -42 to -1) if fT3 and fT4 values are outside the above-mentioned cut-off criteria.

7. Orbital MRI assessment available confirming the diagnosis of TED for patients initially presenting with hypo- or euthyroidism (without treatment for hyperthyroidism) before or at the time of TED diagnosis (to rule-out other potential causes of the orbital signs and symptoms).

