### 8.3.3 Diplopia grading

Diplopia will be graded according to the Gorman score/subjective diplopia score (Bahn et al 1987). This assessment, which is also called "Bahn-Gorman Score" comprises 4 different grades:

- 0 = No diplopia
- 1 = Intermittent diplopia (i.e., diplopia in primary position of gaze when tired or when first awakening)
- 2 = Inconstant diplopia
- 3 = Constant diplopia

A change of one grade will be considered to be clinically relevant.

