## Plan B

The **CAS response** and the **overall response** will be analyzed using the same methodology as for the primary endpoint.

The mean change from baseline in CAS, the mean change from baseline in proptosis and the mean change from baseline in GO-QoL score will be analyzed using a mixed model for repeated measures (MMRM) with factors treatment group and stratum and with baseline as a covariate. Least-square mean differences with corresponding confidence intervals and p-values will be calculated for each visit time point as estimates for the treatment effect.

The proportion of patients achieving response in diplopia and the proportion of patients with an improvement in disease severity at Week 16 will be analyzed analogous to the primary endpoint.

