2.1 Data analysis general information

The data will be analyzed by Novartis and/or a designated clinical research organization (CRO). Any data analysis carried out independently by the investigator should be submitted to Novartis before publication or presentation.

Statistical analysis of all data will be performed using SAS[®] statistical software (SAS Institute, Cary, NC, USA) version 9.4 or higher.

General descriptive statistical rules

Categorical data will be presented as frequencies and percentages. In general, missing values are not considered for calculation of percentages (i.e., adjusted percentages are calculated) if not otherwise specified.

For continuous data, the number of non-missing observations, mean, standard deviation, median, minimum, and maximum will be presented.

Unless otherwise stated, summary tables/figures/listings (TFLs) will be presented for each treatment arm in the respective analysis set.

General information on treatment arm handling, decimal places and other output-related information will be specified in TFL shells accompanying this analysis plan.

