2.2 Analysis sets

Mis-randomized patients who never received any study drug are considered as screen failures and are not included in the analysis sets.

Efficacy analysis

- The **Full analysis set (FAS)** will consist of all patients to whom study treatment (AIN457 or placebo) has been assigned. Following the intent-to-treat principle, patients will be analyzed according to the treatment they have been assigned to.

Safety analysis

The **Safety analysis set (SAF)** will consist of all patients who received at least one dose of study treatment during the treatment period. Patients will be analyzed according to the study treatment received.

Table 2-3 Treatment groups for safety analysis

Analysis period	Treatment group label
DBTP (up to Week 16)	AIN457 Placebo
Entire study period	AIN457 ¹ Placebo ² Any AIN457 ³

1 All patients randomized to secukinumab: This includes responders who receive no treatment after Week 16 and secukinumab non-responders or relapsers who go on open-label secukinumab.

2 Patients randomized to placebo with no open-label treatment in follow-up period. Any AEs reported in placebo patients prior to switching to AIN457 are also counted in this group.

3 Any AIN457 does not refer solely to just patients randomized to AIN457. It includes all patients who received at least one dose of secukinumab in DBTP or open-label follow-up. AEs occurring in placebo patients after switching to AIN457 are counted in this group.

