2.6 Analysis of the secondary objective

2.6.1 Secondary endpoint

The secondary objectives and endpoints are given in [Table 1-1](#).

Analysis of secondary endpoints will be done based on the FAS.

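### The diplopia response rate counts patients with no Baseline diplopia as certain non-responders, so it mixes Baseline prevalence with response; add n/N among patients with Baseline grade 1 or higher

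*SAP*

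**What the plan says.** SAP 1.2, Table 1-1, endpoint 2.3 is the "Proportion of patients achieving response in diplopia at Week 16 defined as follows", and the definition that follows is "Baseline diplopia > 0 and a reduction of ≥ 1 grade with no corresponding deterioration (≥ 1 grade worsening) in the fellow eye". Protocol Tables 2-1 and 2-2 carry the same definition, so the SAP and protocol do not conflict.

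On the denominator, SAP 2.6.1 states: "Analysis of secondary endpoints will be done based on the FAS". Under SAP 2.2 the FAS "will consist of all patients to whom study treatment (AIN457 or placebo) has been assigned", with no condition on Baseline diplopia. SAP 2.1 adds: "In general, missing values are not considered for calculation of percentages". SAP 2.6.3 does not replace missing secondary values. Protocol 12.5.1 says that diplopia response "will be analyzed analogous to the primary endpoint".

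On entry, "Inconstant or constant diplopia" is one of four features in inclusion criterion 3 (Protocol 5.1), and any two are enough.

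On the scale, Protocol 8.3.3 says: "Diplopia will be graded according to the Gorman score/subjective diplopia score". It lists grades 0 to 3, where 0 means no diplopia, and none of the grade descriptions refers to an eye.

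**The concern.** Baseline grade 0 is an observed value, so the missing-value rule does not remove these patients. They enter the denominator as non-responders and cannot be told apart from patients who had diplopia and did not improve. By contrast, every patient must have a CAS of at least 4 in the study eye at entry, so everyone can achieve the 2-point fall that the CAS response needs.

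Two things follow. If the drug helps patients with diplopia, the tabulated difference is smaller than the effect in the patients who could benefit. If the arms differ by chance in how many patients have diplopia at Baseline, the rates differ even when the drug does nothing. Randomisation is stratified by smoking only, and the SAP's descriptive table makes no adjustment. In a report without testing, the percentage is itself the result, and it cannot be interpreted unless the number at risk of response is shown.

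The fellow-eye condition also needs a sentence. Protocol 8.3.3 reads as one grade per patient, while the endpoint refers to worsening in one eye.

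**Working it through.** **Plan's own figures.** The documents give no figure for diplopia. The only planning calculation is for the primary endpoint (Protocol 12.8.1). It reproduces: 60% versus 20%, two-sided 0.05, 90% power and the continuity correction give 35 per arm, and the power at 35 is 0.908 against the stated 0.90. It has no bearing on this point beyond supplying illustrative rates.

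**Inputs.**
- From the documents: 28 patients randomised 1:1 and 25 completing the double-blind period (SAP 1).
- Assumed: 14 per arm with all values observed (the split is not given); Baseline diplopia prevalence π from 0.4 to 0.8; response rates r among patients with Baseline diplopia. The documents give neither π nor r.

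**Formula.** Grade-0 patients contribute no responders, so

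rate over the FAS = π × r.

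**Dilution.** With equal π in both arms, the difference over the FAS is π × (r₁ − r₀). Borrowing 60% and 20% from the primary endpoint:

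| π | FAS rates | FAS difference | Difference among Baseline grade ≥ 1 |
|---|---|---|---|
| 0.8 | 48% vs 16% | 32 points | 40 points |
| 0.6 | 36% vs 12% | 24 points | 40 points |
| 0.5 | 30% vs 10% | 20 points | 40 points |
| 0.4 | 24% vs 8% | 16 points | 40 points |

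**Chance imbalance with no drug effect.** Take r = 40% in both arms, with 9 of 14 versus 5 of 14 having Baseline diplopia:
- 0.4 × 9/14 = 25.7%
- 0.4 × 5/14 = 14.3%
- gap = 0.4 × 4/14 = 11.4 points

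Among patients with Baseline diplopia, the expected rate is 40% in both arms.

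**How often.** For two independent binomial counts of 14, the probability of a difference in either direction is:

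| π | 3 or more patients | 4 or more patients |
|---|---|---|
| 0.4 | 0.335 | 0.176 |
| 0.5 | 0.345 | 0.185 |
| 0.6 | 0.335 | 0.176 |
| 0.7 | 0.301 | 0.147 |

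**Price of restricting the denominator.** In the 9-versus-5 example with no drug effect, the root-mean-square spurious difference is:
- over 14 per arm: √[(9 × 0.24 + 5 × 0.24)/14² + 0.114²] = √(0.0171 + 0.0131) = 0.17
- over 9 and 5: √(0.24/9 + 0.24/5) = √0.0747 = 0.27

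The restricted percentage is centred correctly but is noisier in percentage points.

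**Fellow-eye clause.** If there is one grade per patient, a fall of at least one grade already excludes a rise of at least one grade. The clause is then always met when the rest of the definition is met, and it changes no patient's status.

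**The case against.** The strongest case on the other side is that little rests on this endpoint. It was never in the testing sequence (Protocol 12.4.2), the study stopped early, and SAP 2.6.2 plans only descriptive summaries with no test. The 9-versus-5 split is chosen for illustration. Over randomisation the expected spurious gap is zero, and the restricted rate is noisier. The definition comes from the protocol, and replacing it in an amendment written after termination would be a post hoc change. All of this stands. It argues for adding a line rather than replacing the endpoint, and for low severity. It does not make the single FAS percentage interpretable.

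A reader might infer more than the documents support:

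- *Every randomised patient is in the denominator.* SAP 2.1 and 2.6.3 leave missing values out, and three of the 28 patients had not completed the double-blind period at termination. The denominator is FAS patients with observed data.
- *The fellow-eye condition cannot be evaluated, or biases the rate.* Protocol 8.3 says that efficacy is assessed in both eyes, and Protocol 8.3.5 refers to an ophthalmological manual that is not among the documents. Per-eye recording is therefore open, and under a single grade the clause is merely redundant.
- *New diplopia in a grade-0 patient is never shown.* SAP 2.6.2 plans summaries by visit and change from Baseline, and output details are left to table shells that are not available. The responder endpoint itself does not show it, but another table might.

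**Conclusion.** The point holds as a low-severity reporting weakness. As written, the rate for endpoint 2.3 equals Baseline diplopia prevalence times response among patients with diplopia. At a prevalence of 0.5, a 40-point difference among those patients appears as 20 points. With about 14 per arm, an imbalance of 4 or more patients has probability 0.15 to 0.19 for prevalence 0.4 to 0.7, and in the worked example an imbalance of 4 produces 11.4 points with no drug effect. These sizes rest on the assumed even split, complete data, prevalences and response rates. The multiplication itself rests only on the definition and the analysis set. With equal prevalence there is dilution and no change of sign.

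**What to change.** Keep the protocol-defined rate and state its denominator. Beside it, show by arm:

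1. n/N responders among FAS patients with Baseline diplopia grade 1 or higher and an observed Week 16 grade, with no replacement of missing values;
2. the number of FAS patients with Baseline grade 0 who have diplopia at Week 16.

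Add one sentence on the fellow-eye condition: if only one grade per patient is recorded, it is redundant and has no effect; otherwise, state how the per-eye grade is derived. Record the additions in SAP Section 4 (Change to protocol specified analyses).

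The cost is a few lines of SAP wording and two lines in one table shell, using grades already scheduled at Baseline and Week 16. The downside is that the restricted percentage rests on fewer patients and is noisier, so it should be read with its n/N and not alone.
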